8. SAFETY EVALUATION

8.1. Overview of Safety Analysis Methods

All safety analyses will be performed using the safety population.

Safety measures summarized will include AEs, laboratory data, and vital signs. Additionally, exposure to study treatment during the study will be displayed.

Key adverse event summaries will also be presented by dose as described in Section 8.3.

Safety data will not be imputed, except for partial and missing dates, which will be imputed only for defining treatment-emergent AEs (TEAEs) and concomitant medications. Imputed dates will not be presented in data listings.

TEAEs will be defined as any AEs that occur or are reported to worsen in severity on or after the date of first dose of study treatment. Partial dates will be imputed for the purposes of defining TEAEs as follows:

- For a missing start day where the month and year are present, the start day will be set to the first day of the month, unless 1) the first day of the month is before the date of first dose of study treatment and the month and year are the same as the month and year of the date of first dose of study treatment, and 2) the end date is on or after the date of first dose of study treatment or the end date is completely missing, in which case the start day will be set to the first day of first dose of study treatment.
- For a missing start day and month where the year is present, the start day and month will be set to January 1st, unless 1) January 1st is before the date of first dose of study treatment and the year is the same as the year of the date of first dose of study treatment, and 2) the end date is on or after the date of first dose of study treatment or the end date is completely missing, in which case the start day and month will be set to that of the date of first dose of study treatment.
- For a missing end day where the month and year are present, the end day will be set to the last day of the month, unless the month and year are the same as the month and year of the last contact date for the subject, in which case the end day will be set to that of the subject's last contact date.
- For a missing end day and month where the year is present, the end day and month will be set to the subject's last contact date, unless the year of the subject's last contact date is greater than the end year, in which case the end day and month will be set to December 31st.

Partial and completely missing dates will be imputed for the purposes of classifying concomitant medications as follows:

- Partial dates will be imputed following the same algorithm as above for TEAEs.

- For a missing start date (i.e., day, month, and year are missing), the start date will be set to the date of first dose of study treatment, unless the stop date is prior the date of first dose of study treatment, in which case the start date will be set to the stop date.
- For a missing stop date (i.e., day, month, and year are missing), the medication will be treated as ongoing.

8.2. Extent of Exposure

The following summaries will be displayed overall and by maximum dose of adrulipase received during the study.

Time on treatment (days) will be calculated as: date of last dose of study drug – date first dose of study drug + 1. Time on treatment will be summarized using descriptive statistics for subjects in the safety population. Time on treatment will also be displayed separately for each dose (e.g. time on low dose [1.2 g/day], time on medium dose [1.95 g/day], time on high dose [2.4 g/day]).

For each dose, whether the subject started dosing at that dose level, reason for dose increase (for doses after initial dose), and date/time of first and last dose at that dose level will be listed for all subjects in the safety population.

8.3. Adverse Events

Summaries will be presented overall and by dose. Subjects are classified by maximum dose of adrulipase received during the study.

Adverse events will be coded using the Medical Dictionary for Regulatory Activities (MedDRA) Version 25.1 to identify the system organ class and preferred term.

Adverse events that occur or are reported to worsen in severity on or after date of first dose of study treatment will be considered TEAEs. Adverse events that occurred after the end date of the end of the treatment period will be classified as follow-up adverse events.

TEAEs will be summarized for all subjects in the safety population. The total number of TEAEs occurring will be shown. The number and percentage of subjects experiencing any TEAE will also be provided. In addition, summary tables will reflect a count and percentage of subjects experiencing at least 1 TEAE in each system organ class and preferred term. All percentages will use the number of subjects in the safety population as the denominator. Therefore, if a subject has more than 1 AE within a system organ class, the subject will be counted only once in that system organ class. If a subject has more than 1 AE that codes to the same preferred term, the subject will be counted only once for that preferred term. Tabular summaries will be sorted by descending frequency by system organ class and by preferred term.

TEAEs will also be summarized by maximum relationship to study drug and maximum severity. Relationship to study treatment will be scored as Related or Unrelated. Severity will be rated as Mild, Moderate, or Severe. Summary tables will reflect a count and percentage of subjects experiencing at least 1 TEAE in each system organ class, preferred term and either relationship or severity. If a subject experiences more than 1 AE within a system organ class or preferred term, that subject will be counted only once for that event under the maximum severity or most

related category for the study drug. Similarly, if relationship or severity data are missing, the study analysis will follow the assumption of maximum relationship or severity in the summary tables. These summaries will be presented with percentages that use the number of subjects in the safety population as the denominator. The tabular summaries will be sorted by descending frequency by system organ class and by preferred term.

AE duration (days) is calculated as AE end date – AE start date + 1. Imputed AE start dates and imputed AE end dates as defined in Section 8.1 are used in the case of partially missing dates. AE duration will be presented in the listings.

All AEs will be presented in data listings for subjects in the safety population.

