7 STUDY OBJECTIVES

7.1 Primary Objectives

The Primary objective of this pilot study is to establish safety and efficacy of a new enteric microgranule formulation of adrulipase in patients with EPI due to CF.

The primary safety objective of this study is to assess the safety and tolerability of the highest dose received of adrulipase (for subjects under Part 1, 1.2 g/day, 1.95 g/day or 2.4 g/day; for subjects under Part 2, 3.3 g/day) provided in size 00 capsules containing ~150 mg adrulipase. Efficacy will be evaluated by comparing CFA values during treatment with the highest dose of adrulipase versus baseline CFA obtained during screening of the patient's pre-study porcine PERT.

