8.4.2 Method of Assigning Patients to Adrulipase Treatment

For Part 1, all eligible patients will first start on the low dose (1.2 g/day) and optimize to medium or high dose if required.

For Part 2, all eligible patients will be assigned to adrulipase 3.3 g/day dose.

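### Part 1 adverse events are tabulated only under the highest adrulipase dose a patient ever reached, not the dose at onset, and the TEAE period has no stated end

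*SAP*

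**What the plan says.** **Dose columns.** SAP 8.3 presents adverse event summaries overall and by dose, and says of the dose columns: "Subjects are classified by maximum dose of adrulipase received during the study". SAP 8.4 applies the same rule to serious events, discontinuations and deaths. Neither section has a rule that uses the dose being taken when the event began.

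**Dosing.** Protocol 8.4.2 states: "For Part 1, all eligible patients will first start on the low dose (1.2 g/day) and optimize to medium or high dose if required". Protocol 8.1 describes escalation from low to medium and from medium to high. For the later cohort, Protocol 8.4.2 states: "For Part 2, all eligible patients will be assigned to adrulipase 3.3 g/day dose".

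**TEAE period.** SAP 8.3 states: "Adverse events that occur or are reported to worsen in severity on or after date of first dose of study treatment will be considered TEAEs". SAP 8.1 gives the same lower bound, also without an upper one. The next sentence of SAP 8.3 adds: "Adverse events that occurred after the end date of the end of the treatment period will be classified as follow-up adverse events".

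**Exposure.** SAP 8.2 displays time on treatment separately for each dose. It also provides that the "date/time of first and last dose at that dose level will be listed for all subjects in the safety population".

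**Objective.** Protocol 7.1 sets the primary safety objective as being to "assess the safety and tolerability of the highest dose received of adrulipase".

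**The concern.** In a titration design, a patient's highest dose is known only after the earlier doses have been taken. If all of a patient's events go to that dose, events from the lower-dose days move into the top column. The lower columns keep only the patients who never escalated, although every treated Part 1 patient was exposed to 1.2 g/day.

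Three features of the plan make this matter for reading the tables:

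- Protocol 11.3 says safety will be analyzed by the treatment actually received. For an event that began before escalation, the maximum-dose column does not show that.
- Protocol 11.2 speaks of observing safety for each dose, and Protocol 8.1.1 relies on tolerability at 1.2 to 1.95 g/day to omit titration in Part 2. The planned event tables show little of what this study adds at those doses.
- SAP 8.2 splits exposure by actual dose while SAP 8.3 and 8.4 do not split events that way, so the exposure and event tables do not line up.

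The second issue is the end of the TEAE period. Under Protocol 10.2 adverse events are recorded until the end of the study, which includes about a week back on porcine PERT. If that week counts as treatment-emergent, events on PERT enter the adrulipase dose columns.

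**Working it through.** The plan gives no figure on this point to reproduce. The check is a reading of the definitions followed by day counts.

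**1. Where an event lands.** Take a Part 1 patient with an event on Day 2 at 1.2 g/day who later reaches 2.4 g/day. Under SAP 8.3 the event is a TEAE and appears in the 2.4 g/day column. The 1.2 g/day column contains neither the event nor the patient.

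**2. Who is in each column.** Protocol 6.7 reports 6 Part 1 patients enrolled, of whom 5 had been dosed at 2.4 g/day. At that time the 2.4 g/day column would hold 5 patients, and the two lower columns would share 6 − 5 = 1.

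**3. Lower-dose days behind a 2.4 g/day patient.** Inputs:

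- Treatment period T = 21 days and follow-up F = 7 days (Protocol 8.1, both approximate).
- Days at low dose L and at medium dose M. These are assumed, because escalation depends on symptoms and, at the first step, on discussion with the investigator.
- Schedule (a): 3 + 3 days, taken as the earliest from the three-day symptom rule. Schedule (b): 5 + 5 days, switching after the Day 5 and Day 10 telephone visits.

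Lower-dose share of treatment days = (L + M) / T. Share not at 2.4 g/day if follow-up counts as treatment-emergent = (L + M + F) / (T + F).

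| Schedule | Days below 2.4 g | Days at 2.4 g | Share of treatment days | Share if follow-up is counted |
|---|---|---|---|---|
| (a) 3 + 3 | 6 | 15 | 6/21 = 29% | 13/28 = 46% |
| (b) 5 + 5 | 10 | 11 | 10/21 = 48% | 17/28 = 61% |

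These are shares of days. They become shares of events only if the event rate is constant over time and dose, which the documents do not support.

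**4. Part 2.** With one fixed dose, L + M = 0 and no event can be attributed to the wrong dose.

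**5. End of the TEAE period.** Read alone, the TEAE definition runs to the end of follow-up. The week on PERT would then be 7/28 = 25% of the Part 1 window and, if the same rule is carried to Part 2, 7/21 = 33% there. Read together with the follow-up sentence, those events may instead form a separate class, and the shares are zero. The SAP does not say whether the two classes exclude each other, does not define the date that ends the treatment period, and describes no table of follow-up events.

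**The case against.** The case for leaving the plan alone is substantial.

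- **The rule fits the objective.** Protocol 7.1 is framed on the highest dose received, and the SAP sets maximum-dose classification as a general convention in section 4 and uses it throughout. This stands, and it is why the maximum-dose table should stay. It does not explain why that should be the only by-dose view of events when exposure is split by dose.
- **The information is available.** All adverse events are listed, dose-level dates are listed, and time at each dose is displayed. With about six Part 1 patients, dose at onset can be worked out patient by patient. This is true and limits the harm, but it leaves the reader to build the table.
- **Dose at onset is not a cleaner estimate of a dose effect.** A delayed or cumulative effect would be credited to whichever dose was being taken, and the low dose always comes first. This stands. The additional table describes events and does not remove the confounding of dose with time.
- **The size is uncertain.** Switch times are assumed. Worsening EPI, the trigger for escalation, is not recorded as an adverse event unless it is serious (Protocol 10.1.1), so one obvious source of lower-dose events lies largely outside these tables. Protocol 6.7 also says that no adverse events had been reported, so at that time there was nothing to misplace. All of this stands.

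A reader might also infer that events after the return to PERT are counted against the top adrulipase dose. The documents do not support that as fact, because the sentence after the TEAE definition puts post-treatment events in a class of their own. What remains is an ambiguity.

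**Conclusion.** The point holds for Part 1, as a gap in presentation. The by-dose event tables attribute events that began at 1.2 or 1.95 g/day to a higher dose reached later, and they leave most exposed patients out of the lower-dose columns. Under the two assumed schedules, 29% to 48% of the treatment days behind a 2.4 g/day patient were at a lower dose. That range rests on a 21-day period and the assumed switch times.

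It should not be read as saying that the event rate at 2.4 g/day is overstated by that amount, which would need a constant event rate. Nor do the lower columns show nothing: a patient whose maximum dose was also the dose at onset is placed correctly. Part 2 is not affected.

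The TEAE end is a separate and smaller point. Events in the week back on PERT may or may not enter the dose columns, and the SAP should say which. The 46%, 61%, 25% and 33% figures apply only if they do.

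For a small descriptive pilot with full listings this does not threaten the study. The change is worth making because it is cheap and brings the event tables into line with the exposure tables.

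**What to change.** **In SAP 8.3 and 8.4**, add a Part 1 TEAE table by dose at onset:

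- columns for 1.2, 1.95 and 2.4 g/day;
- as denominator for each column, all Part 1 patients who received that dose;
- patient-days at each dose shown beside the counts;
- dose at onset derived from the dose-level dates and times in SAP 8.2;
- a stated rule for events with a partial onset date. The imputation in SAP 8.1 can move such an event to the first-dose date, and so into the 1.2 g/day column.

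Keep the maximum-dose table alongside it, since it answers the objective in Protocol 7.1.

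**In SAP 8.1 and 8.3**, state that TEAEs end at a defined date tied to the last adrulipase dose, and that follow-up adverse events are excluded from TEAEs and tabulated separately.

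**Cost.** SAP wording, one derivation and a small number of extra tables, with no new dose-date collection. Patients will appear in more than one column of the new table, so its columns cannot be added up, and dose stays confounded with time on study. A footnote should say both.

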8.4. Deaths, Serious Adverse Events, and Other Significant Adverse Events

Summaries will be presented overall and by dose. Subjects are classified by maximum dose of adrulipase received during the study.

Treatment-emergent SAEs, TEAEs leading to treatment discontinuation, TEAEs leading to study discontinuation and TEAEs resulting in death will be summarized for all subjects in the safety population.

Summary tables will reflect a count and percentage of subjects experiencing at least 1 TEAE in each system organ class and preferred term within each AE subset (serious, leading to treatment discontinuation, leading to study discontinuation, resulting in death). These tabular summaries will be sorted by descending frequency by system organ class and by preferred term.

SAEs, adverse events leading to treatment discontinuation, adverse events leading to study discontinuation, and AEs resulting in death will be presented in data listings for subjects in the safety population.

8.5. Clinical Laboratory Evaluation

All summaries except for the shift tables will be presented overall and by dose. Subjects are classified by maximum dose of adrulipase received during the study.

Values at Screening (Visit 1) and at 3 weeks post first dose, as described in Section 3, for laboratory parameters for hematology, clinical chemistry, and urinalysis will be summarized for the safety population using descriptive statistics.

Shift tables based on classification of values with respect to the reference range (low, normal, high) will be summarized for the safety population for critical clinical chemistry and hematology laboratory tests.

Post-baseline elevations in alanine aminotransferase (≥ 3 times the upper limit of normal [ULN]), aspartate aminotransferase (≥ 3 times ULN), total bilirubin (≥ 1.5 times ULN) will be summarized at Screening and at 3 Weeks Post First Dose. Hematology, clinical chemistry, hepatic monitoring, urinalysis, lipids, and pregnancy results will be presented in data listings for subjects in the safety population.

8.6. Vital Signs, Physical Findings, and Other Observations Related to Safety

8.6.1. Vital Signs

Summaries will be presented overall and by dose. Subjects are classified by maximum dose of adruclipase received during the study.

Values at Screening (Visit 1), Screening (Visit 2, during supervised confinement), and at 3 Weeks Post First Dose (Visit 6), as described in Section 3, of systolic blood pressure, diastolic blood pressure, heart rate, respiratory rate, and temperature will be summarized for the safety population using descriptive statistics.

Vital sign values will be presented in a data listing for all subjects in the safety population.

8.6.2. Physical Examinations

A focused physical examination evaluating gastrointestinal tract, heart, and lungs will be performed at study visits 2, 6, and 9. An indication of whether the examination was performed (yes/no), date of the examination, and an indication of whether abnormal findings that were clinically significant were found (yes/no) will be collected. Because details of clinically significant abnormal findings will be entered on the medical history or AE form as appropriate, this data will be summarized with medical history and AEs, respectively.

9. ENDPOINT EVALUATION

9.1. Overview of Efficacy Analysis Methods

9.1.1. Multicenter Studies

Data from all sites will be pooled for the purpose of analyses.

9.1.2. Assessment Time Windows

No assessment time windows will be used for analyses.

9.1.3. Timing of Analyses

The final analysis will occur after last subject completes Visit 7 (follow-up) or terminates early from the study.

9.1.4. Multiple Comparisons/Multiplicity

No statistical testing is planned for the efficacy endpoints for this single arm study. Thus, no adjustments are needed for multiplicity.

9.2. Primary Endpoint

The primary endpoint analyses will be presented overall and by dose. Subjects are classified by maximum dose of adrlipase received during the study.

9.2.1. Computation of the Primary Endpoint

The primary efficacy endpoint is defined as the CFA assessed at the end of the 3-week treatment period (Visit 6, on adrlipase). CFA is evaluated by the 72-hour marker-to-marker stool sample collection at Visit 6 and standardized high-fat diet during supervised confinement. Coefficient of fat absorption represents the percentage of fat absorbed from the diet by the subject and is calculated from the results of the quantitative fecal fat measurement in conjunction with the dietary fat intake.

CFA will be calculated by using 2 data points:

- Fat consumption in grams/24h (converted from fat consumption in grams/72h as provided by the qualified dietician at each site).
- Fat excretion in grams/24h as provided by the central laboratory.

CFA will be calculated as follows:

$$\frac{(\text{Grams}/24\text{h of fat consumed} - \text{Grams}/24\text{h of fat excreted}) \times 100}{\text{Grams}/24\text{h of fat consumed}}$$

9.2.2. Primary Analysis of the Primary Endpoint

The primary analysis of the primary endpoint will be a comparison of the mean CFAs from the adrulipase treatment vs the PERT treatment (screening), using descriptive statistics. The primary efficacy endpoint analysis will use the mITT population. For the summary of CFA, if a subject switches back to PERT during the confinement period, prior to the end of the stool collection, then the CFA value will be excluded from the summary.

Values and change from baseline (Visit 2, on PERT) to end of treatment (Visit 6, on adrulipase) in stool weights will be summarized using descriptive statistics. Summaries will be performed for the overall group and by maximum dose of adrulipase received using descriptive statistics.

In addition, the number and percentage of subjects in the mITT population who have a CFA \geq 80% based on the CFA at week 6 (3-week post dose) will be summarized.

Fat consumed (g/24h), fat excreted (g/24h), and CFA (%) at each visit as well as CFA change from baseline to end of treatment will be listed for all subjects in the mITT population.

Details of each supervised confinement, including controlled diet and marker-to-marker stool collection, will be listed for all subjects in the mITT population.

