The mean CFA for the MS1819 group was 56% (range 7% to 92%), and the mean CFA for the PERT group was 86% (range 57% to 97%). This mean CFA of 56% on a dose of 2240 mg/day MS1819 was similar to the mean CFA of 62% in the chronic pancreatitis study at the same dose. The mean coefficient of nitrogen absorption (CNA) for the MS1819 group was 93% and the mean CNA for the PERT group was 97%. Symptoms of exocrine pancreatic insufficiency were more prominent in the MS1819 group.

MS1819 was well-tolerated, with no remarkable adverse events. Three SAEs occurred during the screening period, but none during the study itself. Each of these SAEs was due to pulmonary exacerbations of cystic fibrosis. Laboratory values were unremarkable during the study.

6.6.4 *AZ-CF2002: A Phase 2, Open-Label, Multicentre, 2x2 Crossover Study to assess the Safety and Efficacy of MS1819 in Enteric Capsules in Patients with Exocrine Pancreatic Insufficiency due to Cystic Fibrosis; with an Extension Phase Evaluation of Immediate-Release MS1819 Capsules*

This study, referred to as the OPTION 2 study, was the second experience with MS1819 in patients with cystic fibrosis. The study began in August of 2020, and all patients completed the study by April 2021. The study was conducted in 9 sites, with 5 in the U.S. and 4 in Poland. All sites participated in enrollment.

The primary objectives of the study were to assess the safety and efficacy of MS1819 in enteric capsules vs porcine pancreatic enzyme replacement therapy (PERT) in patients with exocrine pancreatic insufficiency (EPI) due to cystic fibrosis (CF). The safety and tolerability of MS1819 treatment (2240 and 4480 mg/day; enteric capsules) were assessed during the crossover phase, as was efficacy by comparing coefficient of fat absorption (CFA) percentages across the MS1819 (2240 and 4480 mg/day) versus porcine PERT treatment groups. The exploratory objective during the dose extension phase was to identify immediate-release MS1819 (4.4 or 6.7 g/day) doses that were safe and resulted in CFA percentages residing within the current PERT therapeutic range. The study was not powered for inferential statistics. A total of at least 30 patients were planned to complete the study.

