11 STATISTICAL METHODS

11.1 General Considerations

The statistical methods will be further detailed in the Statistical Analysis Plan (SAP).

Any change to the data analysis methods described in the protocol will require an amendment only if it changes a principal feature of the protocol. Any other change to the data analysis methods described in the protocol, and the description for making the change, will be described in the SAP and in the clinical study report. Additional exploratory analyses of the data will be conducted as deemed appropriate.

Statistical methodology and analyses will be in accordance with the principles outlined by the International Council for Harmonisation (ICH) E9 guidelines.

Tables, listings, and figures will be produced in accordance with the principles outlined by the ICH E3 guidelines.

Summaries will consist of descriptive statistics including the nonmissing counts, mean, standard deviation, median, Interquartiles (IQ), minimum and maximum values for continuous variables, and number and percentage of patients in each defined category for categorical variables.

The primary efficacy endpoint analysis aims to compare the mean CFA after receiving adrulipase vs porcine PERT. With the sample size to be employed, primary efficacy analysis will be descriptive rather than inferential.

As a general rule, missing data will not be replaced.

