3.4. Sample Size

Based upon CFA data obtained in the recently completed Phase 2 studies (OPTION, OPTION 2), 12 patients using a dose titration scheme should provide sufficient point estimates of CFA and all other secondary efficacy endpoints. Given the acceptable safety profile obtained in the previous Phase 2 OPTION studies, a sample of 12 patients should be adequate for observation of safety.

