4. GENERAL ANALYSIS AND REPORTING CONVENTIONS

The following is a list of general analysis and reporting conventions to be applied for this study.

Categorical variables will be summarized using counts (n) and percentages (%) and will be presented in the form “n (xx.x).” If a count is 0, 0% will be shown for the percentage. To ensure completeness, summaries for categorical and discrete variables will include all categories, even if no subjects had a response in a particular category.

Continuous variables will be summarized using mean, SD, minimum, maximum, median and number of subjects. The 25th and 75th percentiles will be provided for distributions that are known to be skewed. The mean, median, 25th percentile, 75th percentile, and confidence intervals (CI) will be reported to 1 more level of precision than the original observations, and the SD will be reported to 2 more levels of precision than the original observations. The minimum and maximum will be the same precision as the original data.

When p-values are provided, they will be rounded to 3 decimal places; p-values that round to “0.000” will be presented as “<0.001.” Unless otherwise stated, all statistical tests of treatment effects will be conducted at a 2-sided alpha level of 0.05.

All analysis will be performed using SAS® System version 9.4 or later.

Dates in listings will be displayed as yyyy-mm-dd (e.g., 2023-01-24).

The baseline value is defined as the last non- missing value on or before the first dose of study treatment.

Select displays will be presented by dose (1.2 g/day, 1.95 g/day, 2.4 g/day). Subjects will be classified by the maximum dose of adrulipase received during the study.

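### SAP 9.2.2 plans no confidence interval for mean CFA, the within-patient CFA change or the ≥80% rate, and its only summary of change names stool weights instead of CFA

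*SAP*

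**What the plan says.** **Primary analysis.** SAP 9.2.2 describes it as "a comparison of the mean CFAs from the adrulipase treatment vs the PERT treatment (screening), using descriptive statistics", and protocol 11.7.1 says the same. SAP 9.2.2 adds the number and percentage of patients with CFA of at least 80%.

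**Meaning of descriptive statistics.** SAP 4 states: "Continuous variables will be summarized using mean, SD, minimum, maximum, median and number of subjects". It adds quartiles for distributions known to be skewed. Protocol 11.1 states: "Summaries will consist of descriptive statistics including the nonmissing counts, mean, standard deviation, median, Interquartiles (IQ), minimum and maximum values". Neither list includes a standard error or an interval.

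**Intervals.** In SAP 4, "confidence intervals (CI) will be reported to 1 more level of precision than the original observations". This is a rounding rule. No CFA analysis in SAP 9 asks for an interval.

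**Change in CFA.** In SAP 9.2.2 the sentence on visit values and change from Visit 2 to Visit 6 names stool weights, which SAP 9.3.1 covers again. CFA change appears only in the patient listing. For nitrogen absorption (CNA), SAP 9.3.3 does summarise values and change, although protocol 11.7.2 says CNA is handled as CFA is.

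**Inferential status.** Protocol 11.1 says the "primary efficacy analysis will be descriptive rather than inferential". SAP 4 carries a general convention that "all statistical tests of treatment effects will be conducted at a 2-sided alpha level of 0.05", but SAP 9.1.4 plans no efficacy test.

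**Sample size.** SAP 3.4 says "12 patients using a dose titration scheme should provide sufficient point estimates of CFA". It gives no SD and no precision target.

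**The concern.** The stated efficacy objective (protocol 7.1) compares each patient's CFA on adrulipase with the same patient's CFA on pre-study PERT. The natural estimate is therefore the mean within-patient difference, and its precision depends on the SD of that difference. The planned tables give two marginal means with their SDs. The SD of the difference cannot be recovered from those without the correlation between the two visits. The summary that would have supplied it appears to have been written for the wrong variable.

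The result will also be read against 80%, which is the sponsor's target (protocol 6.7) and a planned responder cut-off. With about 12 patients in total, split by Part (protocol 11.7.1) and by maximum dose (SAP 9.2), the sampling error of a mean or a percentage may be large. The plan as written would not show it beside the estimate.

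**Working it through.** The plan states no precision figure, so there is none to reproduce. The steps below show what an interval would look like.

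**Inputs**
- Target total: about 12 completers (protocol 8.3.1).
- Already in Part 1 when protocol version 2.0 was written: 6 (protocol 6.7). By subtraction, Part 2 has 12 − 6 = about 6.
- Protocol 11.2 instead plans 12 for each dose. Both n = 6 and n = 12 are therefore shown.
- SD of CFA on adrulipase: not given. OPTION (protocol 6.6.3) reports a mean of 56% and a range of 7% to 92%, with 41 enrolled and 32 completing.

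**Assumed SD.** The range is 92 − 7 = 85 points. Under normality, the expected range is 4.139 SDs for n = 32 and 4.341 SDs for n = 41. This gives 85/4.139 = 20.5 and 85/4.341 = 19.6. The rule of thumb range/4 gives 21.3. I use 20, with 15 to 25 as the range.

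**Half-width for the Visit 6 mean:** t(0.975, n−1) × SD/√n
- n = 12, SD 20: 2.201 × 20/√12 = 12.7
- n = 6, SD 20: 2.571 × 20/√6 = 21.0
- n = 12, SD 15 to 25: 9.5 to 15.9
- n = 6, SD 15 to 25: 15.7 to 26.2

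**Within-patient change.** SD_change = √(s_A² + s_P² − 2·r·s_A·s_P), where s_A and s_P are the SDs on adrulipase and on PERT and r is their correlation. The documents give none of these. For illustration, take s_A = 20.5, s_P from 5 to 10 and r from 0 to 0.5. The upper s_P matches OPTION's PERT range, (97 − 57)/4.139 = 9.7; a smaller value is plausible because entry requires CFA of at least 80% on PERT. SD_change then runs from 17.8 to 22.8. The half-width is 11.3 to 14.5 at n = 12 and 18.6 to 23.9 at n = 6.

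**Proportion with CFA ≥80%.** Clopper-Pearson limits are the 0.025 quantile of Beta(x, n−x+1) and the 0.975 quantile of Beta(x+1, n−x).
- 3/6: 12% to 88%
- 6/12: 21% to 79%

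The best-case and worst-case summaries in SAP 9.2.4 address dropouts. They do not address this sampling error.

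**The case against.** The best defence is that this is an openly descriptive pilot with no test, success threshold or decision rule, so an interval would change no stated decision. That is true, and it limits the weight of the point. It is not a reason to leave intervals out, because an interval is estimation and needs neither a p-value nor a multiplicity adjustment.

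SAP 2 places table specifications in a separate document, and the SAP abbreviations include CI and SE, so the table shells may carry intervals. That cannot be checked here. What can be said is that the SAP text does not require them.

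A reader might infer three stronger things that the documents do not support:

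- **That the means come with no measure of uncertainty.** SD, minimum, maximum and n are planned, and each patient's CFA and change are listed. The interval for each mean can be rebuilt from SD and n, and the paired interval from the listing. What is missing is a planned interval and a summary of CFA change.
- **That Part 2 will have about 6 patients and an interval of ±21.** The 6 is a subtraction that conflicts with protocol 11.2, and ±21 also needs the assumed SD. The OPTION spread may not carry over to a formulation designed to overcome acid inactivation. CFA cannot exceed 100%, yet 80 + 21 = 101, so a symmetric interval with SD 20 is doubtful near the target.
- **That a small-sample mean could not be told apart from 56% or from 80%.** At ±21, a mean of 80 gives 59 to 101, which excludes 56, and a mean of 56 gives 35 to 77, which excludes 80. Only means from 80 − 21 = 59 to 56 + 21 = 77 are compatible with both. At ±12.7 that band shrinks to 67.3 to 68.7. The 56% figure is also background; the planned comparator is the patient's own PERT value.

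**Conclusion.** The point holds as a reporting gap in the primary analysis. The SAP text assigns no interval to mean CFA, to the within-patient change or to the ≥80% rate, and as worded it does not summarise CFA change at all. The stool-weight wording in SAP 9.2.2 is probably a copying slip, since SAP 9.3.1 repeats that summary and CNA receives the one that CFA lacks.

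The size is conditional. With an SD of about 20, assumed from a different formulation and dose, the Visit 6 mean carries about ±13 points at n = 12 and ±21 at n = 6. The figures for change rest on further assumptions and are only illustrative. The responder intervals depend only on the counts used as examples. Because no decision rule depends on these results, this is a worthwhile and cheap correction, not a threat to the trial's validity.

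**What to change.** 1. **SAP 9.2.2:** correct the change sentence so that it covers CFA. Make the headline estimate the mean within-patient change (Visit 6 minus Visit 2, patients with both values) with a two-sided 95% t-interval. Present it by Part once the SAP is updated to protocol version 2.0.
2. **SAP 9.2.2:** add a 95% interval for the Visit 6 mean and a Clopper-Pearson 95% interval for the proportion with CFA of at least 80%. Keep the median, range and patient listing beside them, given the ceiling at 100%.
3. **SAP 9.3.3:** give CNA change an interval in the same way.
4. **SAP 3.4 and protocol 11.2:** replace the claim that the point estimates will be sufficient with the expected 95% half-width and the SD assumed for it.
5. **Protocol synopsis, 8.3.1 and 11.2:** reconcile about 12 patients in total with 12 for each dose, and state the planned Part 2 number.

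No p-values are needed, and the analysis stays descriptive. The cost is some wording and a few extra table columns. The SAP was written from protocol version 1.0 and does not contain Part 2, so it needs revision in any case. The one drawback is that the stated precision will look less favourable.
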